## 9. Reporting adverse events

### List of abbreviations

AE: Adverse Event

CA: Competent Authority

EC: Ethics Committee

SAE: Serious Adverse Event

SSAR: Suspected Serious Adverse Reaction

SUSAR: Suspected Unexpected Serious Adverse Reaction

### Adverse events (AE)

The following information will be recorded:

- nature of adverse event;
- date and time of occurrence and disappearance;
- intensity: mild, moderate or severe;
- frequency: once, continuous or intermittent;
- decision regarding study: continuation or withdrawal;
- relation to the study medication (see below).

AE's will be recorded from the first drug administration until the end of the trial.

Special attention will be given to those subjects who have discontinued the trial for an AE, or who experienced a severe or a serious AE.

### Definitions of Adverse Event (AE)

Any untoward medical occurrence in a patient or clinical investigation subject administered a pharmaceutical product and which does not necessarily have a causal relationship with this treatment. An adverse event (AE) can therefore be any unfavorable and unintended sign (including

an abnormal finding), symptom, or disease temporally associated with the use of a medicinal (investigational) product, whether or not related to the medicinal (investigational) product.

*Serious Adverse Event (SAE)*

Any untoward medical occurrence that at any dose:

- results in death;
- is life-threatening;
- requires inpatient hospitalization or prolongation of existing hospitalization;
- results in persistent or significant disability/incapacity;

or

- is a congenital anomaly/birth defect.

Note: Medical and scientific judgement should be exercised in deciding whether expedited reporting is appropriate in other situations, such as important medical events that may not be immediately life-threatening or result in death or hospitalization but may jeopardize the subject or may require intervention to prevent one of the outcomes listed in the definition above.

*Unexpected adverse event*

An adverse event, the nature or severity of which is not consistent with the applicable product information (e.g., Investigator's Brochure for an unapproved investigational product or package insert/summary of product characteristics for an approved product).

*Life-threatening*

Any event in which the subject was at risk of death at the time of the event; it does not refer to an event which hypothetically might have caused death if it were more severe.

*Associated with the use of the drug*

An adverse event is considered associated with the use of the drug if the attribution is possible, probable or definitive.

Attribution definitions

*Not related*

An adverse event which is not related to the use of the drug.

*Unlikely*

An adverse event for which an alternative explanation is more likely - e.g. concomitant drug(s), concomitant disease(s), and/or the relationship in time suggests that a causal relationship is unlikely.

*Possible*

An adverse event which might be due to the use of the drug. An alternative explanation - e.g. concomitant drug(s), concomitant disease(s), - is inconclusive. The relationship in time is reasonable; therefore the causal relationship cannot be excluded.

*Probable*

An adverse event which might be due to the use of the drug. The relationship in time is suggestive (e.g. confirmed by dechallenge). An alternative explanation is less likely - e.g. concomitant drug(s), concomitant disease(s).

*Definitely*

An adverse event which is listed as a possible adverse reaction and cannot be reasonably explained by an alternative explanation - e.g. concomitant drug(s), concomitant disease(s). The relationship in time is very suggestive (e.g. it is confirmed by dechallenge and rechallenge).

Reporting of adverse events

Adverse events will be reported between the first dose administration of trial medication and the last trial related activity.

All AEs and SAE's will be recorded in the patient's file and in the CRF. All SAE's will be reported as described below.

Medical events that occur between signing of the Informed Consent and the first intake of trial medication will be documented on the medical and surgical history section and concomitant diseases page of the CRF.

SAE's occurring within a period of 30 days following the last intake of trial medication will also be handled as such if spontaneously reported to the investigator.

All serious adverse events (SAE) and pregnancies occurring during clinical trials must be reported by the local Principal Investigator within 24 hours after becoming aware of the SAE to:

- The local EC;
- HIRUZ Clinical Trial Unit (CTU) of the University Hospital Ghent;
- The National Coordinating Investigator (in case of multicenter trials);

This reporting is done by using the appropriate SAE form. For the contact details, see below.

It is the responsibility of the local Principal Investigator to report the local SAE's to the local EC.

In case the National Coordinating investigator decides the SAE is a SUSAR (Suspected Unexpected Serious Adverse Reaction), HIRUZ CTU will report the SUSAR to the Central EC and the CA within the timelines as defined in national legislation. The National Coordinating Investigator reports the SUSAR to all local Principal Investigators and to MSD.

In case of a life-threatening SUSAR the entire reporting process must be completed within 7 calendar days. In case of a non life-threatening SUSAR the reporting process must be completed within 15 calendar days.

The first report of a serious adverse event may be made by telephone, e-mail or facsimile (FAX).

Contact details of HIRUZ CTU:

e-mail: [[contact]](mailto:[contact])

[contact]

[contact]

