### 6.1.6 Advantages and disadvantages for the participants

In Belgium anti-TNF $\alpha$  treatment for axSpA is only reimbursed for patients with sacroiliitis on MRI according to ASAS and an elevated CRP. In this trial the European guidelines are used, so participants qualify for treatment with anti-TNF $\alpha$  if they have sacroiliitis on MRI (according to ASAS definition) or an elevated CRP (they do not have to meet both criteria) [11]. Up until now Golimumab is not reimbursed in Belgium for the treatment of axSpA. Thus, this means an advantage for the participants.

As all the investigations and treatments in this trial are considered routine clinical care, there are no specific disadvantages for the participants.

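### Adverse event recording opens only at the first dose of an undefined trial medication, so early complications of the pre-treatment ileocolonoscopy are filed as medical history

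*Combined protocol and SAP*

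**What the plan says.** Section 9 states the start of AE collection twice. Under Adverse events (AE): "AE's will be recorded from the first drug administration until the end of the trial". Under Reporting of adverse events: "Adverse events will be reported between the first dose administration of trial medication and the last trial related activity". The same subsection says that medical events "between signing of the Informed Consent and the first intake of trial medication will be documented on the medical and surgical history section" and on the concomitant diseases page of the CRF.

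For serious adverse events (SAEs) it adds: "All serious adverse events (SAE) and pregnancies occurring during clinical trials must be reported by the local Principal Investigator within 24 hours" of awareness. It also says that "SAE's occurring within a period of 30 days following the last intake of trial medication will also be handled as such" if they are reported spontaneously. The definitions in section 9 describe an AE as "Any untoward medical occurrence in a patient or clinical investigation subject administered a pharmaceutical product", and define an SAE as such an occurrence at any dose. Section 13 has the ethics committee receive reports of adverse events that are serious, unexpected and linked to the study.

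Consent is signed at screening (section 6.2.1). All subjects then have an ileocolonoscopy before treatment, and NSAID treatment starts at baseline (section 6.2.2). Golimumab starts only if the response target is not met at week 4. Section 6.1.6 lists perforation among the risks of the study procedures, and also says that "all the investigations and treatments in this trial are considered routine clinical care".

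**The concern.** The ileocolonoscopy is the invasive procedure of this trial, and part of the tissue sampling is done for research. A rule that sends everything between consent and first dose to the history pages takes early complications of that procedure out of the AE record, although they arise from something the protocol requires.

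The rule also depends on a term that is never defined. Section 9 speaks of a first drug, of trial medication and of study medication. Two sites could open the AE window at different times, one at the first NSAID dose and one at the first golimumab injection, and their safety data would not be comparable. The annual safety report described in section 9, which must summarise the safety of the trial subjects, would draw on those records.

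**Working it through.** No figure in the plan bears on this point, so there is none to reproduce. The check sets the passages in order of time and tests each reading.

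**1. Order of events.** Consent (screening, 6.2.1), then ileocolonoscopy (pre-treatment, 6.2.2), then first NSAID dose (baseline, 6.2.2), then golimumab (from week 4, NSAID non-responders only, 6.2.2). The AE window opens at a first dose. Whichever drug is meant, the procedure falls after consent and before the window opens. A complication that starts in that interval goes to the history pages.

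**2. Does the routine-care argument cover the whole procedure?** Section 6.2.2 itself separates routine from extra biopsies:

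- Routine pathology: 4 + 8 = 12.
- RNA sequencing, all sites: 2 + 2 = 4.
- Functional analyses, Ghent only: 6 + 6 = 12.
- Research biopsies outside Ghent: 4 of 12 + 4 = 16. In Ghent: 4 + 12 = 16 of 12 + 4 + 12 = 28.

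So some of the sampling is done for the trial and not for care.

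**3. Serious events before the first dose.**

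| Text | Points towards |
|---|---|
| 24-hour clause, section 9: all SAEs during the trial, no first-dose limit | expedited reporting |
| Section 13: serious, unexpected and linked to the study | ethics committee report, no first-dose limit |
| Definitions, section 9: AE tied to an administered product, SAE to any dose | not an AE or SAE |
| Pre-dose rule, section 9: history and concomitant diseases pages | not an AE |

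These texts are not reconciled. A site could follow either pair and point to the protocol.

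**4. What is trial medication?**

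| | Golimumab only | NSAIDs included |
|---|---|---|
| Supporting text | Medication column of the study table (6.4); study medication in drug accountability (6.5.10) | NSAIDs listed under Medication (6.5); first drug administration in section 9 |
| Switched patients | NSAID phase outside the window: week 4 − week 0 = 4 weeks, visits within 2 weeks either way | covered from the first NSAID dose |
| Never-switched patients | no window at all, including any remission ileocolonoscopy (6.2.4) | covered from the first NSAID dose |
| 30-day SAE rule | no last intake to count from if never switched | works |
| Remaining gap | consent to first golimumab dose | consent to first NSAID dose; short after the procedure, since both are listed under baseline (6.2.7.2) |

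For patients who receive golimumab, the second ileocolonoscopy falls inside the window on either reading, because reporting runs to the last trial-related activity.

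**The case against.** The case on the other side is substantial.

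- Opening AE collection at first dose agrees with the protocol's own AE definition, and pre-dose events are not lost: they stay in the CRF. This stands. The loss is from AE counts, not from the record.
- The protocol calls the procedure standard of care. This stands for the ileocolonoscopy and the 12 routine biopsies, but not for the extra ones.
- A reader might infer that pre-dose SAEs are excluded from expedited reporting. The documents do not support that. The 24-hour clause has no first-dose limit, and section 13 is tied to the study and not to the drug. Equally, neither settles the matter: the SAE definition refers to a dose, and perforation is already named in section 6.1.6 and so might not count as unexpected. Unreconciled is as far as the text goes.
- A reader might also infer that the NSAID phase is plainly outside AE recording. That holds only on the golimumab-only reading. The first drug given under the protocol is an NSAID, section 6.5 lists NSAIDs first, and the word intake suits an oral drug at least as well as an injection.
- The plan has no safety objective or endpoint (sections 3.1 to 3.5), and section 10.3 specifies no AE table. This lowers the stakes, but section 9 still requires AE records and an annual safety summary.
- A field for relation to a study procedure is a preference. The nature and timing of each event are already recorded, and the CRF is not among the documents.

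**Conclusion.** The point holds and is minor. One part does not depend on how the terms are read: a complication of the baseline ileocolonoscopy that begins before the first dose is documented as history and not counted as an AE. Two parts are ambiguities to be resolved: the handling of serious pre-dose events, and the meaning of trial medication.

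The size cannot be stated as a number of events or patients. If NSAIDs count, the gap after the procedure is short. If only golimumab counts, it is about 4 weeks for a patient who switches at week 4, and the whole of follow-up for one who never does.

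Three further inferences are tempting and unsupported:

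- **A count of never-switched patients.** Section 6.1.1 plans 147 and section 10.1 needs 110 in the golimumab arm; 147 − 110 = 37. But 110 is a required number, not a guaranteed minimum of switchers, so more than 37 could stay on NSAIDs. The step from 110 to 147 is also unexplained: 110 / 0.75 = 146.7, which rounds up to 147, would equally fit a 25% drop-out allowance. So 37 is neither an estimate nor an upper bound, and no patient-week total should be built on it.
- **A share of risk.** 4 of 16 and 16 of 28 are shares of biopsies. The documents give no complication rate and no separate risk for biopsies.
- **An effect on efficacy.** No efficacy endpoint depends on the AE window.

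**What to change.** In section 9:

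1. Record AEs and SAEs related to study procedures from informed consent, and keep the history page for conditions present before consent.
2. State that serious procedure-related events before the first dose follow the existing 24-hour route, and bring the definitions, the reporting text and section 13 into line with that.
3. Define trial medication and use one term in sections 6.5.10 and 9. Word the AE window and the 30-day SAE rule so that they cover the NSAID phase and patients who never start golimumab.

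A field for relation to a study procedure, beside relation to study medication, is optional.

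The cost is amendment wording and a notice to sites, plus a small form change if the optional field is added. The downside is a few more AE entries and slightly higher reported counts. No dose, visit or treatment rule changes.

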### Annual Safety Reporting

HIRUZ CTU will ask the National Coordinating Investigator for an annual report containing an overview of all SSARs (Suspected Serious Adverse Reaction) and a summary regarding the safety of the trial subjects. HIRUZ CTU will send this report to the Central EC and the CA within the timelines as defined in national legislation. The National Coordinating Investigator will pass this annual report to all local Principal Investigators.

## 10.2 Analysis of the images and the samples

Central reading will be performed by the departments Rheumatology and Radiology of the Ghent University Hospital ( dr. [name] and prof. dr. [name]). Radiological images of patients enrolled at Reuma Institute Hasselt (Center 02) and at Imelda hospital Bonheiden (center 03), will be pseudonymized and uploaded on an electronic device (eg. external HDD). At the end of the trial, the electronic device with all the pseudonymized images will be send by secured postal mail to the Rheumatology department of Ghent University Hospital to allow for central reading.

The blood samples, stool samples and gut biopsies will finally all be stored in the prospective research biobank of the department of rheumatology of the Ghent University Hospital ("Biobank van menselijk lichaamsmateriaal van patiënten met reumatische en/of musculoskeletale aandoeningen en gezonde controles", EC 2019/0314, medical administrator: prof. dr. [name]). For the Imelda Hospital in Bonheiden (Center 03) these biological samples will first be stored on site as part of the prospective research biobank of the department of rheumatology of the Ghent University Hospital and shipped regularly in batch to the Gent University Hospital. The gut biopsies from patients recruited at the Reuma Institute Hasselt (Center 02) will be collected at Jessa Hospital, will be registered and stored (temporarily) in the Jessa Biobank (medical administrator: dr. [name] – no processing required except for immediate freezing) and will be transferred at once (cooled transport at -80°C) to the prospective research biobank of the department of Rheumatology of Ghent University Hospital after the study has ended. Subsequently all samples will be analysed by the laboratory attached to the department of Rheumatology of the Ghent University Hospital (Medical Research Building, MRB) and by the VIB. These are to investigate e.g. the serum and fecal calprotectin levels and to perform in depth immunophenotyping (flow cytometry). Reuma Institute Hasselt, Jessa Ziekenhuis Hasselt nor Imelda hospital Bonheiden is expected to perform any analyses on any of the additionally collected study samples.

## 10.3 Statistical analysis

The statistical analysis will be performed by the department of Rheumatology of the Ghent University Hospital in collaboration with the department of Biostatistics of the Ghent University.

## 11. Insurance

Faultless liability Ghent University.

## 12. Publication policy

The results of this trial will be published in an A1-journal. The privacy of the participants will be respected at all times.

## PART 2: GENERAL PART OF THE PROTOCOL

### **13. Independent Ethics Committee (IEC) / Institutional Review Board (IRB)**

This trial can only be undertaken after full approval of the protocol and addenda has been obtained from the IEC/IRB. This document must be dated and clearly identify the protocol, amendments (if any), the informed consent form and any applicable recruiting materials and subject compensation programs approved. During the trial, the following documents will be sent to the IEC/IRB for their review:

- reports of adverse events that are serious, unexpected and associated with the study
- all protocol amendments and revised informed consent form (if any)

Amendments should not be implemented without prior review and documented approval/favorable opinion from the IEC/IRB except when necessary to eliminate an immediate hazard to trial subjects or when the change involves only logistical or administrative aspects of the trial. At the end of the trial, the investigator will notify the IEC/IRB about the trial completion.

### **14. ICH/GCP guidelines**

This trial will be conducted in accordance with the protocol, current ICH-GCP guidelines and applicable law(s). Good Clinical Practice (GCP) is an international ethical and scientific quality standard for designing, conducting, recording and reporting trials that involve the participation of human subjects. Compliance with this standard provides public assurance that the rights, safety and well-being of trial subjects are protected, consistent with the principles that have their origin in the Declaration of Helsinki, and that the clinical trial data are credible.

### **15. Subject information and informed consent**

Prior to entry in the trial, the investigator must explain the procedure of the trial and the implication of participation to potential subjects or their legal representatives. Subjects will be informed that their participation is voluntary and that they may withdraw consent to participate at any time. Participating subjects will be told that competent authorities and authorized persons may access their records without violating the confidentiality of the subject, to the extent permitted by the applicable law(s) and/or regulations. By signing the Informed Consent Form (ICF), the subjects or legally acceptable representatives are authorizing such access. After this explanation and before entry to the trial, written, dated and signed informed consent should be obtained from the subject or legally acceptable representative. The ICF should be provided in a language sufficiently understood by the subject. Subjects must be given the opportunity to ask questions. The subject or legally acceptable representative will be given sufficient time to read the ICF and to ask additional questions. After this explanation and before entering the trial, consent should be appropriately recorded by means of either the subject's or his/her legal representative's dated signature or the signature of an independent witness who certifies the subject's consent in writing. After having obtained the consent, a copy of the ICF must be given to the subject. In case the subject or legally acceptable representative is unable to read, an impartial witness must attest the informed consent.

### **16. Case Report Forms**

The source documents are to be completed at the time of the subject's visit. The CRFs are to be completed within reasonable time after the subject's visit. The investigator must verify that all data entries in the CRFs are accurate and correct. If certain information is Not Done, Not Available or Not Applicable, the investigator must enter "N.D." or "N.AV." or "N.AP", respectively in the appropriate space.

## **17. Direct access to source data/documents**

The investigator will permit trial-related monitoring, audits, IRB/IEC review, and regulatory inspection(s), providing direct access to source data/documents.

## **18. Data handling and record keeping**

The investigator essential documents will be retained for at least 20 years. At that moment, it will be judged whether it is necessary to retain them for a longer period, according to applicable regulatory or other requirement(s).

